### 10.19. Appendix 19: Liver Safety: Suggested Actions and Follow-up Assessments

#### 10.19.1. Stopping Algorithm

Study intervention will be discontinued for a participant if liver chemistry stopping criteria are met.

#### Phase 2 Liver Chemistry Stopping Criteria and Increased Monitoring Algorithm (no preexisting liver disease)

#### 10.19.2. Follow up Assessments

#### Phase 2 Liver Chemistry Stopping Criteria and Follow-up Assessments

Phase 2 liver chemistry stopping criteria are designed to assure participant safety and to evaluate liver event etiology. In patients with alternative clinical reasons for elevated liver enzymes (for example, patients experiencing exercise induced CPK elevation or cholelithiasis), rechallenge with investigational product may be possible after discussion with medical monitor.

Liver Chemistry Stopping Criteria	
ALT/AST-absolute	ALT or AST- $\geq 5 \times \text{ULN}$
ALT/AST-Increase	
If cannot monitor: ALT or AST- <math>\geq 3 \times \text{ULN}</math> and cannot be monitored weekly for 4 weeks
 
Or if able to monitor: ALT or AST- <math>\geq 3 \times \text{ULN}</math> persists for <math>\geq 4</math> weeks

Total bilirubin	ALT or AST- $\geq 3 \times \text{ULN}$ and total bilirubin $\geq 2 \times \text{ULN}$ (or at least a doubling of direct bilirubin in known Gilbert's syndrome)
INR^2	ALT or AST- $\geq 3 \times \text{ULN}$ and international normalized ratio (INR) $> 1.5$ , if INR measured
Symptomatic	ALT or AST- $\geq 3 \times \text{ULN}$ associated with symptoms (new or worsening) believed to be related to liver injury or hypersensitivity
Suggested Actions, Monitoring and Follow-up Assessments	
Actions	Follow-up Assessments

 
• Immediately stop study intervention
 
• Report the event to the sponsor within 24 hours
 
• Complete an SAE form^2
 
• Perform follow-up assessments as described in the Follow Up Assessment column
 
• Monitor the participant until liver chemistry test abnormalities resolve, stabilize, or return to baseline (see MONITORING)
 
 
MONITORING:  If ALP <math>< 2 \times \text{ULN}</math>, ALT or AST- <math>\geq 3 \times \text{ULN}</math> AND total bilirubin <math>\geq 2 \times \text{ULN}</math> (or at least a doubling of direct bilirubin in known Gilbert's syndrome) or INR <math>> 1.5</math> (if measured):
 
 
• Repeat liver chemistry tests (include ALT, aspartate transaminase [AST], alkaline phosphatase, total and direct bilirubin and INR) and perform liver event follow-up assessments within 24 hours
 
• Monitor participant twice weekly until liver chemistry test abnormalities resolve, stabilize, or return to baseline
 
• A specialist or hepatology consultation is recommended
 
 
If ALT or AST- <math>\geq 3 \times \text{ULN}</math> AND total bilirubin <math>< 2 \times \text{ULN}</math> and INR <math>\leq 1.5</math>:
 
 
• Repeat liver chemistry tests (include ALT, AST, alkaline phosphatase, total and direct
 
	
 
• Viral hepatitis serology
 
• Obtain INR and recheck with each liver chemistry assessment until the transaminases values show downward trend
 
• Obtain blood sample for pharmacokinetic (PK) within 1 week of the event of ALT or AST <math>\geq 3 \times \text{ULN}</math>
 
• Obtain serum creatine phosphokinase (CPK), lactate dehydrogenase (LDH), gamma-glutamyltransferase [GGT], glutamate dehydrogenase [GLDH], and serum albumin
 
• Fractionate bilirubin
 
• Obtain complete blood count with differential to assess eosinophilia
 
• Record the appearance or worsening of clinical symptoms of liver injury, or hypersensitivity, on the CRF as per CRF completion guidelines
 
• Record use of concomitant medications (including acetaminophen, herbal remedies, recreational drugs and other over-the-counter medications)
 
• Record alcohol use on the CRF as per CRF completion guidelines
 


bilirubin and INR) and perform liver chemistry follow-up assessments within 24 to 72 hours
 
 
• Monitor participants weekly until liver chemistry abnormalities resolve, stabilize, or return to baseline
 
 
RESTART/RECHALLENGE
 
 
• If liver event causality is determined to be “not related”, restart may be permitted upon written approval of the sponsor. See restart guidelines
 
	
If ALT or AST ≥3xULN AND total bilirubin ≥2xULN or INR >1.5 (if measured) obtain the following in addition to the assessments listed above:
 
 
• Anti-nuclear antibody, anti-smooth muscle antibody, Type 1 anti-liver kidney microsomal antibodies, and quantitative total immunoglobulin G (IgG) or gamma globulins
 
• Serum acetaminophen adduct assay, when available, to assess potential acetaminophen contribution to liver injury in participants with definite or likely acetaminophen use in the preceding week
 
• Liver imaging (ultrasound, magnetic resonance, or computerized tomography) and/or liver biopsy to evaluate liver disease; complete CRF as per CRF completion guidelines
 
• Liver biopsy may be considered and discussed with local specialist if available:             
 
– In participants when serology raises the possibility of autoimmune hepatitis (AIH)
 
– In participants when suspected DILI progresses or fails to resolve on withdrawal of study intervention
 
– In participants with acute or chronic atypical presentation
 
 
 
• If liver biopsy conducted complete CRF as per CRF completion guidelines
 

---	---

1. Serum bilirubin fractionation should be performed if testing is available. If serum bilirubin fractionation is not immediately available, discontinue study intervention if ALT ≥3xULN **and** total bilirubin ≥2xULN. Additionally, if serum bilirubin fractionation testing is unavailable, **record the absence/presence of detectable urinary bilirubin on dipstick** which is indicative of direct bilirubin elevations suggesting liver injury.
2. All events of ALP <2 x ULN, ALT **or** AST- ≥3 x ULN **and** total bilirubin ≥2xULN (or at least a doubling of direct bilirubin in known Gilbert’s syndrome) or ALP <2 x ULN , ALT **or** AST- ≥3 x ULN **and** INR >1.5 (if measured) may indicate severe liver injury (**possible ‘Hy’s Law’**) **and must be reported to sponsor in an expedited manner and as an SAE if SAE criteria are met (excluding studies of hepatic impairment or cirrhosis)**. The INR stated threshold value will not apply to participants receiving anticoagulants.
3. New or worsening symptoms believed to be related to liver injury (such as fatigue, nausea, vomiting, right upper quadrant pain or tenderness, or jaundice) or hypersensitivity (such as fever, rash or eosinophilia).

4. Includes: hepatitis A immunoglobulin M (IgM) antibody; HBsAgG and HBcAB; hepatitis C RNA; cytomegalovirus IgM antibody; Epstein-Barr viral capsid antigen IgM antibody (or if unavailable, heterophile antibody or monospot testing); and hepatitis E IgM antibody.
5. PK sample may not be required for participants known to be receiving placebo or non-comparator interventions. Record the date/time of the PK blood sample draw and the date/time of the last dose of study intervention prior to the blood sample draw on the CRF. If the date or time of the last dose is unclear, provide the participant's best approximation. If the date/time of the last dose cannot be approximated OR a PK sample cannot be collected in the time period indicated above, do not obtain a PK sample. Instructions for sample handling and shipping are in the laboratory manual.

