#### **Serious Adverse Events**

All serious adverse events, as well as PQC, occurring during the study must be reported to the appropriate sponsor contact person by study-site personnel within 24 hours of their knowledge of the event.

Serious adverse events, including those spontaneously reported to the investigator within 12 weeks after the last administration of study intervention, must be reported using the Serious Adverse Event Form. The sponsor will evaluate any safety information that is spontaneously reported by an investigator beyond the time frame specified in the protocol.

A possible Hy's law Case is defined by the occurrence of alanine transaminase/aspartate transaminase  $\geq 3$  x upper limit of normal (ULN), alkaline phosphatase  $< 2$  x ULN together with total bilirubin  $\geq 2$  x ULN or international normalized ratio  $> 1.5$  (if measured). Any possible Hy's Law case is considered an important medical event and should be reported to the sponsor in an expedited manner, even before all other possible causes of liver injury have been excluded.

Information regarding SAEs will be transmitted to the sponsor using the Serious Adverse Event Form and Safety Report Form of the CRF, which must be completed and reviewed by a physician from the study site and transmitted to the sponsor within 24 hours. The initial and follow-up reports of an SAE should be transmitted electronically or by facsimile (fax). Telephone reporting should be the exception and the reporter should be asked to complete the appropriate form(s) first.

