### **ADDITIONAL ELEMENTS, WHERE APPLICABLE:**

- Certain protocol-mandated visits to the study site may not be possible during the COVID-19 outbreak. Therefore, temporary measures may be implemented if considered appropriate by the sponsor and investigator to maintain continuity of patient care and study integrity. Certain measures, such as those listed below, may be necessary and should be instituted in accordance with applicable (including local) laws, regulations, guidelines, and procedures:
  - remote (eg, by phone / telemedicine) or in-person, off-site (e.g. in-home) interactions between site staff (or designees) and patients for study procedures e.g. those related to safety monitoring / efficacy evaluation / study drug storage and administration (including training where pertinent)

[figure not shown]
- procurement of study drug by patients (or designee) or shipment of study drug from the study site directly to patients for at-home administration (including the potential for patient self-administration of study drug)
- laboratory assessments using a suitably accredited local laboratory; for selected measures (e.g. urine pregnancy), home testing may be employed
- other procedures, eg, imaging, may be conducted at an appropriate facility
- Missed assessments/visits will be captured in the clinical trial management system for protocol deviations. Discontinuations of study interventions and withdrawal from the study should be documented with the prefix “COVID-19-related” in the CRF.
  - other relevant study data elements impacted by the pandemic should also be documented / labeled as “COVID-19-related” in CRFs and / or other study systems, as directed by detailed sponsor guidance. These may include missed / delayed / modified study visits / assessments / dosing, and instances where temporary measures such as those above are implemented.
- The sponsor will evaluate the totality of impact of COVID-19 on collection of key study data and additional data analyses will be outlined in study SAP(s).
- Precaution: for those who may carry a higher risk for severe COVID-19 illness (e.g. those aged over 65 years), follow guidance from local health authorities when weighing the potential benefits and risks of enrolling in the study, and during participation in the study.

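### Appendix 19, footnote 1 to the Total bilirubin stopping row omits AST although the row names ALT or AST, so a site could read the footnote as narrowing a mandatory stop

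*Protocol*

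**What the plan says.** Protocol Section 10.19.1 makes the stop mandatory: "Study intervention will be discontinued for a participant if liver chemistry stopping criteria are met".

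The table in Section 10.19.2 then lists the criteria. Its Total bilirubin row, which carries footnotes 1 and 2, begins "ALT or AST- $\geq 3 \times \text{ULN}$ and total bilirubin" and sets the bilirubin threshold at ≥2×ULN. For known Gilbert's syndrome it gives an alternative, at least a doubling of direct bilirubin. Footnote 1 reads: "If serum bilirubin fractionation is not immediately available, discontinue study intervention if ALT ≥3xULN", and the same sentence goes on to require total bilirubin ≥2×ULN as well.

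Elsewhere both enzymes are named. That is true of the other transaminase criteria in the table, the monitoring text, the follow-up column and footnote 2 on possible Hy's Law. It is also true of the Hy's Law note in Appendix 3. Section 8.3.1 has a possible Hy's Law case "defined by the occurrence of alanine transaminase/aspartate transaminase" at or above 3×ULN, together with its other conditions.

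**The concern.** Footnote 1 is the only line in this group that names ALT without AST. It sits on a specific row and addresses a specific circumstance, so a site holding an unfractionated result may treat it as the rule for that result. On that reading, a participant whose AST meets the threshold but whose ALT does not would fall outside the stop, although the row includes that participant.

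With alkaline phosphatase below 2×ULN, this is the pattern that footnote 2 flags as possible severe liver injury and requires to be reported in an expedited manner. A mandatory hepatic stop should not depend on which of two lines a site reads. There is also a compliance consequence. SAP Appendix 4 counts as a major deviation a participant who met withdrawal criteria but was not withdrawn, and two differing lines make that classification open to dispute.

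**Working it through.** No plan figure needs reproducing, so the check compares the two conditions. All values are multiples of ULN, and TB is total bilirubin.

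- Row (Section 10.19.2, Total bilirubin): R = (ALT ≥3 or AST ≥3) and TB ≥2
- Footnote 1 (same table): F = ALT ≥3 and TB ≥2
- Absolute row (same table): A = ALT ≥5 or AST ≥5, whatever the bilirubin

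The Gilbert's alternative is left aside, because it rests on direct bilirubin.

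| ALT | AST | TB | Row R | Footnote F | Absolute row A |
|---|---|---|---|---|---|
| 3.5 | 1 | 2.5 | met | met | not met |
| 3.5 | 3.5 | 2.5 | met | met | not met |
| 1 | 3.5 | 2.5 | met | **not met** | not met |
| 2.9 | 4.9 | 2.0 | met | **not met** | not met |
| 1 | 5.5 | 2.5 | met | **not met** | met |
| 3.5 | 1 | 1.5 | not met | not met | not met |
| 1 | 3.5 | 1.5 | not met | not met | not met |

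Step 1. Whenever F is met, R is met. The lines can differ in one direction only: R met and F not met, which is ALT <3, AST ≥3 and TB ≥2.

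Step 2. If AST is ≥5, row A already stops study intervention. The region left is ALT <3, AST 3 to <5, TB ≥2.

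Step 3. Three other rows also act on AST ≥3: INR above 1.5 if measured; symptoms attributed to liver injury or hypersensitivity; and AST ≥3 that either cannot be monitored weekly for 4 weeks or persists for at least 4 weeks. Any of these removes the case from the region.

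Step 4. Footnote 1 applies only when fractionation is unavailable. Appendix 3 lists total and indirect bilirubin in the chemistry panel, so central results should seldom be affected. The likelier setting is Appendix 18, which permits, as a temporary COVID-19 measure, "laboratory assessments using a suitably accredited local laboratory". The documents do not say how often that happens or what such laboratories report.

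The documents give no rate for any of these conditions, so the expected number of participants cannot be calculated.

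**The case against.** The strongest reply is that nothing conflicts. Footnote 1 gives a condition for stopping; it does not say to continue otherwise and does not suspend the row. The row is not conditional on fractionation, which enters it only through the Gilbert's alternative, and Section 10.19.1 makes the row binding. This stands in large part: read together, an AST-driven case meets the row and is stopped. What remains is that a footnote giving a narrower condition for a named circumstance can be taken as the governing rule for that circumstance.

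Four stronger readings are tempting, and the documents do not support them.

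- A reader might infer that footnote 1 stops study intervention on ALT with no bilirubin condition. It does not; total bilirubin ≥2×ULN is required.
- A reader might infer that footnote 1 directs sites to keep dosing AST-driven cases. It is silent on them.
- A reader might count 3 or 4 further weekly doses before the next scheduled 4-weekly chemistry. The monitoring text, which names ALT or AST, calls for repeat chemistry within 24 hours and then twice weekly when bilirubin is ≥2×ULN and alkaline phosphatase is below 2×ULN. The scheduled interval is therefore not a sound basis for a dose count.
- A reader might infer an effect on the primary estimand. A liver-related stop is intercurrent event 3, handled by treatment policy in Protocol Section 9.4.2.1 and SAP Section 5.3.2.1, so it does not by itself change HiSCR50 status.

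The heading for the stopping and monitoring algorithm has no algorithm beneath it in the text available. A figure may be missing and might state the condition. It would not remove the difference between the row and its footnote.

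**Conclusion.** The inconsistency is real and lies in current protocol text, but it is small. The row and footnote 1 state different transaminase conditions for the same stop. They part only in the region found in the working, under a footnote that applies only without fractionation. Such cases should be rare, and their number cannot be derived.

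This rests on two assumptions: that footnote 1 belongs to the row whose superscript it carries, and that no figure outside the available text tells sites which line governs. It is a wording fault in a mandatory safety rule, with no shown effect on the efficacy analysis. It merits correction because a site could read it as narrowing that rule and the correction costs almost nothing. Nothing here says which transaminase condition is clinically right.

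**What to change.** Reconcile the Total bilirubin row and footnote 1 in Section 10.19.2 so that both state the same transaminase condition. The sponsor decides which. Section 8.3.1 and Appendix 3 already name both enzymes and need only a consistency check against the wording chosen.

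The cost is a few words in one place, with a short note to sites if any are still dosing. The SAP introduction records a decision on 14 October 2022 to terminate the study, so most of the remaining value is in the final record and in reuse. Appendix 20 attributes Appendix 19 to an update of the sponsor's template, so the template should be checked for the same wording.

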## 10.20. Appendix 20: Protocol Amendment History

The Protocol Amendment Summary of Changes Table for the current amendment is located directly before the Table of Contents.

### Amendment 1 (08 July 2021)

**Overall Rationale for the Amendment:** The overall rationale for the amendment is to make the FibroTx Patch assessment optional due to the potential unavailability of the FibroTx Patch kits.

Section number and Name	Description of Change	Brief Rationale
1.3 Schedule of Activities (SoA)	Subheaders were added for each SoA as follows: Section 1.3.1. Period 1 and Period 2 (Screening Through Week 16), and Section 1.3.2. Period 3 and Period 4 (Week 17 Through Week 36).	To clarify that the study periods are in 2 SoAs and to align with protocol terminology.
1.3.1 Period 1 and Period 2 (Screening through Week 16)	Footnote m was added to the FibroTx Patch assessment to indicate that participation is optional.	The FibroTx Patch assessment is optional due to the potential unavailability of the FibroTx Patch kits.
1.3.2 Period 3 and Period 4 (Week 17 through Week 36)	Footnote j was added to the FibroTx Patch assessment to indicate that participation is optional.	
8.6 Biomarkers 8.6.1 Skin Biomarkers	It was clarified that the FibroTx Patch assessment is to be collected for participants who consent to this optional part of the study and when kits are available.	
8.6 Biomarkers 8.6.1 Skin Biomarkers	The wound exudate assessment is to be collected only for those participants who have wound exudate.	To clarify that the wound exudate assessment can only be collected for those participants who have wound exudate.
1.3.1 Period 1 and Period 2 (Screening through Week 16)	A vital signs assessment was added to the screening period.	The assessment was inadvertently omitted.
1.3.1 Period 1 and Period 2 (Screening through Week 16)	The Hidradenitis Suppurativa Investigator's Global Assessment was removed from the screening period.	To clarify that this assessment is not needed at screening.
1.3.1 Period 1 and Period 2 (Screening through Week 16)	Serum, plasma, and whole blood sample assessments for biomarkers were added at Week 6.  An Exudate Swab assessment was removed at Week 4 and added at Week 6.  A FibroTx Patch assessment was removed at Week 4 and added at Week 6 in the SoA and in footnote t.	The time points of selected biomarker assessments were updated to support dosing decisions.
1.3.1 Period 1 and Period 2 (Screening through Week 16)  8.2.3 Electrocardiograms	An electrocardiogram was added at Week 16.	To monitor any changes after participants have received study intervention.
1.1 Synopsis  3 Objectives and Endpoints	The endpoints in the Synopsis, and Objectives and Endpoints were updated.	To align on consistent terminology.

Section number and Name	Description of Change	Brief Rationale
2.2 Background	The bermekimab no observed adverse effect level dose exposures maximum concentration and area under the curve for intravenous administration and subcutaneous administration were updated.	To align with the bermekimab Investigator's Brochure (IB).
4.2.1 Study-Specific Ethical Design Considerations  8 Study Assessments and Procedures	The expected total blood volume to be collected from each participant was removed.  A statement was added that the maximum amount of blood drawn per participant will not exceed 500 mL.  Table 1: Volume of Blood to be Collected from Each Participant was removed.	To reduce the site-level operational burden.
5.1 Inclusion Criteria	Inclusion criterion 12 was modified to increase the interval during which the participant agrees not to receive a live virus or live bacterial vaccination after the last administration of study intervention from 5 weeks to 90 days.	To align with the bermekimab IB guidance on the use of live virus or live bacterial vaccination.
5.2 Exclusion Criteria  5.3 Lifestyle Considerations	Exclusion criterion 11 was modified to remove the recommendation on vaccinations in the NOTES on COVID-related exclusion, which was moved to lifestyle considerations.	To clarify that the vaccination recommendations are not intended to be eligibility criteria.
6.7.4 Analgesic Therapy	A statement that participants will not be permitted to use any analgesics related to hidradenitis suppurative pain within 24 hours of a scheduled study visit was removed.	The statement was not applicable because pain is recorded in the participant's diary entries and not assessed at scheduled study visits.
7.1 Discontinuation of Study Intervention  8.2.6 Allergic Reactions	Detailed clinical specifications regarding hypersensitivity reactions were removed.  Revised clinical recommendations for assessing hypersensitivity reactions were consolidated in Section 7.1.	To provide flexibility for clinicians in assessing the severity of hypersensitivity reactions and consolidate clinical recommendations in a single section of the protocol.
8.2.7 Injection-site Reactions	It was specified that participants should be monitored for the occurrence of injection-site reactions for 30 minutes after the study intervention administration.	To clarify the length of time of observation for injection-site reactions.
8.3.1 Time Period and Frequency for Collecting Adverse Event and Serious Adverse Event Information  10.3 Appendix 3: Clinical Laboratory Tests	The parameters and reporting requirements for a possible/potential Hy's Law case were added.	To clarify reporting requirements.
10.6 Appendix 6: Contraceptive Guidance	Bilateral tubal occlusion was updated as an example of tubal closure.	To clarify that other types of tubal closure are considered highly effective, user independent methods of contraception.
10.7 Appendix 7: Hepatitis B Virus (HBV) Screening	Guidelines for hepatitis B screening specific to participants from sites in Japan were added.	To provide guidance and the evaluations to be obtained in the setting of specific patterns of

Section number and Name	Description of Change	Brief Rationale
with HBV DNA Testing		hepatitis B virus test abnormalities in Japan.
10.10 Appendix 10: Hidradenitis Suppurativa Activity and Severity Index (HASI)	The 2018 version of the HASI was replaced with the 2019/2020 version of the HASI.	A new version of the index was received from the developer.
10.17 Appendix 17: Hidradenitis Suppurativa Lesion Monitoring Using Imaging (Visible Light Photography and Medical Infrared Thermography)	The Spectron IR system was removed as an option to perform the lesion imaging.	The Spectron IR system is not available.
10.19 Appendix 19: Liver Safety: Suggested Actions and Follow-up Assessments	An appendix with the liver safety stopping algorithm and follow-up assessments was added.	The sponsor's template was updated to provide guidance and evaluations to be obtained in the setting of specific patterns of liver enzymes abnormalities.
1.3.1 Period 1 and Period 2 (Screening through Week 16)  1.3.2 Period 3 and Period 4 (Week 17 through Week 36)	Acronym definitions were added to the SoA.	The definitions were inadvertently omitted.
Throughout the protocol	Minor grammatical, formatting, or spelling changes were made.	Minor errors were noted.

